### VI.2 Secondary outcomes

1. Percentage of patients who had at least one chest CT (according to billing and EMR data) during the 1-year study period, comparing patients contacted by patient navigator in the intervention group ("as treated" analysis) vs. all patients in control group.
2. Percentage of patients in intervention vs. control groups who had at least one lung CT screening stratified by language spoken, race, age (<> 65 years) and practice site. (subgroup analysis)
3. Of patients whose initial chest CT generated a radiologist's recommendation for early interval follow-up, the percentage who received the recommended follow-up of in timely manner. The timeliness of care is defined by radiologist's recommendation plus additional 30 days. For recommended biopsy/PET scan we chose 60 days limit. All radiologists at MGH use Lung-RADS system to recommend the follow up post LDCT. These standardized recommendations include 12, 6 or 3 months follow up or for suspicious malignancy PET CT vs biopsy. There is some variability in reading diagnostic chest CT; however recommendations are similar to Lung-RADS. At the end of one-year trial a blinded research assistant will review the electronic medical records of patients who had a chest CT during study period. The dates of imaging will be confirmed by billing data.
4. Mean time to follow-up of abnormal results, comparing intervention and control groups.
5. Tobacco treatment use: Percentage of patients, comparing intervention and control groups, who during the 1-year study period had any of the following:
  - o referral to MA Quitline as determined by patients' QuitWorks data or referral scanned in EHR
  - o smoking cessation medication prescribed in EHR (nicotine patch, gum, lozenge, inhaler, nasal spray or bupropion, or varenicline) during the study period
  - o referral to in-person counseling from CHC-based tobacco coach –documented in EHR
6. Percentage of patients, comparing intervention and control groups, who have a status of former or nonsmoker entered in coded field of EHR at the visit closest to the date of 1 year follow-up.
7. Percentage of patients in intervention group who are reached by PN and percentage of patients reached who had lung screening (process measures)

## AIM 3

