### **VI.3. Analytic Methods**

#### **AIM 2:**

We will examine differences in lung screening rates using chi-square tests.

The comparisons include (1) between intervention and control groups (intention-to-treat analysis), and (2) between patients contacted and not contacted by patient navigators (“as-treated” analysis).

An exploratory subgroup analysis will compare lung screening rates between intervention and control groups stratified by language spoken, race, age (<> 65 years), practice site and other factors.

Furthermore, we will use logistic regression models to examine predictors of lung screening, including patient, provider, and practice characteristics.

In addition to comparing the percentage that completed recommended test in a timely manner between intervention and control group using a chi-square test, we will use survival analysis techniques to compare time to completion between intervention and control groups.

We will also use chi-square tests to compare the percentage with referral to MA Quitline, prescription to smoking cessation medications, referral to in person counseling from CHC tobacco coach, and documented smoking status in EHR between intervention and control groups.

For the intervention group, we will document process measures (percentage reached by PN and percentage agreed to have lung screening test within) and present with 95%CI's.

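### Mean time to follow-up is compared between arms in a post-randomisation subset and pooled over recommended intervals, so the mix of recommendations alone can create or hide a difference

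*Combined protocol and SAP*

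**What the plan says.** Two secondary outcomes in VI.2 concern what happens after an abnormal scan. Item 3 is a percentage with a restricted denominator: "Of patients whose initial chest CT generated a radiologist's recommendation for early interval follow-up". Its limit follows the recommendation: "The timeliness of care is defined by radiologist's recommendation plus additional 30 days". For invasive or PET work-up the text says "For recommended biopsy/PET scan we chose 60 days limit". On the range of recommendations it says "These standardized recommendations include 12, 6 or 3 months follow up or for suspicious malignancy PET CT vs biopsy". Diagnostic scans count as well as screening scans: "There is some variability in reading diagnostic chest CT; however recommendations are similar to Lung-RADS".

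Item 4 reads in full: "Mean time to follow-up of abnormal results, comparing intervention and control groups". It makes no reference to the recommended interval and does not define an abnormal result.

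VI.3 (Aim 2) plans "comparing the percentage that completed recommended test in a timely manner between intervention and control group using a chi-square test" for item 3, and survival methods, not further specified, for time to completion. It names no stratification or adjustment by recommended interval or CT type. The only regression model in that section concerns predictors of being screened. The record review takes place at the end of the one-year trial.

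**The concern.** Two separate problems meet in item 4 and in the time-to-completion analysis.

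**Selection.** A patient enters the comparison only after having a chest CT that calls for follow-up. Having a chest CT is the primary outcome (VI.1), and navigation is expected to raise it by at least 5 points (VI.4). The two groups compared are therefore not the groups that were randomised, and they may differ in risk, in reason for the scan and in findings.

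**Pooling.** A PET scan or biopsy falls due within weeks and a repeat scan after 3 or 6 months. A mean over all of them depends on the mix of recommendations as well as on how promptly patients were followed up.

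Helping patients obtain follow-up of abnormal results is a stated navigator task (IV and V.4) and the reason given for the one-year duration (III and VI.4). A difference in mean time will naturally be read as a navigator effect. It could be reported as benefit or as harm when adherence is the same in both arms, or a real benefit could be masked.

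**Working it through.** **Plan's own figure.** None is given for items 3 and 4. The only design figure is 88% power for the primary CT comparison (VI.4). The control rate is not stated. With 400 v 876 patients (1276 − 400), two-sided power for a 5-point difference is 89.2% at a 5% control rate and 85.6% at 6%, so 88% fits a control rate of about 5–6%. This serves below only as one assumption about CT rates.

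**Step 1: spread of intervals, from VI.2 item 3.** Longest time that still counts as timely, taking a month as 30 days:
- PET/biopsy: 60 days
- 3-month: 90 + 30 = 120 days
- 6-month: 180 + 30 = 210 days

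I assume that item 4 covers the same early-follow-up recommendations as item 3, so 12-month recommendations are left out.

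**Step 2: effect of mix on the mean.** Pooled mean = Σ (share of class × mean days in class). If the share in one class rises by 10 points at the expense of another, the change is 0.10 × (difference in class means). With follow-up at the limits above:
- PET/biopsy to 6-month: 0.10 × (210 − 60) = 15 days
- PET/biopsy to 3-month: 0.10 × (120 − 60) = 6 days
- 3-month to 6-month: 0.10 × (210 − 120) = 9 days

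**Step 3: illustration under assumptions.** The documents give no shares, class means or timely rates. Assume mean days of 95 / 185 / 30 and timely rates of 65% / 50% / 85% for 3-month / 6-month / PET-biopsy, the same in both arms.

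| Shift | Mix, intervention | Mix, control | Mean days | Difference | Timely difference |
|---|---|---|---|---|---|
| Mild | 30/50/20 | 35/40/25 | 127.0 v 114.75 | +12.25 | −2.5 points |
| Moderate | 25/60/15 | 35/35/30 | 139.25 v 107.0 | +32.25 | −6.75 points |
| Strong | 20/70/10 | 35/25/40 | 151.5 v 91.5 | +60.0 | −12.75 points |

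Example: 0.25 × 95 + 0.60 × 185 + 0.15 × 30 = 139.25. If the mixes were exchanged between arms, the signs would reverse. If timely rates were equal across classes, the last column would be zero whatever the mix.

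**Step 4: masking.** Add a true benefit of 15 days within every class. The pooled difference becomes 12.25 − 15 = −2.75 days (mild), 32.25 − 15 = +17.25 (moderate) or 60 − 15 = +45 (strong). In the last two the benefit appears as harm.

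**Step 5: false-positive rate.** Simulation with no effect within any class, a within-class SD of 20 days (assumed) and a pooled Welch t-test at nominal 5%, for subsets of 10 v 20, 20 v 40 and 30 v 50:
- mild shift: 9%, 11%, 14%
- moderate: 26%, 44%, 56%
- strong: 65%, 93%, 98%

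Subtracting a class-specific reference interval (90, 180 and an assumed 25 days) brings every scenario back to about 4–5%. The simulation contains no selection within class, so this isolates the pooling component only. For the pooled timeliness percentage under the same assumptions, rejection is 7–10% (moderate) and 11–22% (strong).

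**Step 6: subset size.** Assume CT rates from 10% v 5% to 25% v 20%, with 15–30% of CTs needing early follow-up:
- intervention: 400 × 0.10 × 0.15 = 6, to 400 × 0.25 × 0.30 = 30
- control: 876 × 0.05 × 0.15 ≈ 7, to 876 × 0.20 × 0.30 ≈ 53 (6 to 48 with the 800 controls in the V.4 table)

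At an assumed 75% timely, the 95% half-width for a difference is 1.96 × √[0.75 × 0.25 × (1/n₁ + 1/n₂)], which is 47 points for 6 v 7 and 19 points for 30 v 53.

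**The case against.** **Timeliness is already indexed.** A reader might infer that item 3 is distorted by pooling in the same way as item 4. The documents do not support that. The item 3 limit moves with the recommendation, so with perfect adherence it is 100% in both arms whatever the mix. Pooling matters there only if the chance of timely completion differs between classes, which is unknown. What remains for item 3 is the post-randomisation selection.

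**The survival analysis may turn out to be stratified.** The method is left open; it is not specified as unstratified, and no time origin is given. That is fair. But survival methods as such deal with censoring, not with case mix, and nothing in VI.3 commits the analysis to separating the classes.

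**The case mix by arm is conjecture.** It is tempting to say that control CTs will be mostly diagnostic and navigated CTs mostly screening, and so to predict the direction of bias. Section II says that screening CT was not widely used at the hospital, and navigators steer patients towards it, so the expectation is reasonable. The documents give no CT mix by arm, however, so neither direction nor size can be asserted.

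**Small numbers limit false claims.** With about 10 v 20 patients and a mild shift, a spurious result is only slightly more frequent than nominal (9%). This stands. It means that item 4 may be imprecise as well as biased; imprecision does not remove the bias from the reported estimate.

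**These are secondary outcomes.** Correct. The primary comparison is unaffected.

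**Conclusion.** The point holds for item 4, and for the time-to-completion analysis unless it is stratified. Following the text as written can give a between-arm difference in mean time with identical adherence: about 15 days for each 10-point shift between PET/biopsy and 6-month recommendations. That figure rests on the plan's own timeliness limits, with follow-up taken at those limits. The 12-, 32- and 60-day differences and the rejection rates rest on assumed mixes, class means, SD and subset sizes, and serve only as illustration. The actual size and direction cannot be known from the documents.

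Item 3 is affected less: its limit already follows the recommendation, and only the selection applies without further assumptions. For both items, separating the classes removes the pooling problem but not the selection, so neither comparison can by itself be attributed to navigation. The change should be made before analysis; no primary conclusion depends on it.

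**What to change.** In VI.2 and VI.3:

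1. Replace the pooled mean in item 4 with time from the CT to completion of the recommended follow-up, censored at the end-of-study review. This also settles how patients with no follow-up by then are handled, for which a mean has no stated rule.
2. Show it by Kaplan-Meier within recommendation class (3-month, 6-month, PET/biopsy) and compare arms with a log-rank test stratified by class only.
3. Keep item 3's limits as they stand, show the percentage by class, and use an exact test if expected counts are small.
4. Report CT type (screening or diagnostic) descriptively by arm.
5. State that items 3 and 4 are non-randomised, descriptive comparisons.

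Three further steps are not advisable:
- Stratifying by CT type as well gives 3 × 2 = 6 strata for very few patients, on a factor that navigation may itself change.
- Kaplan-Meier on days past the due date gives negative times for early completers, and PET/biopsy has a 60-day limit but no due date.
- A composite of CT plus all follow-up on time, over everyone randomised, nearly repeats the primary outcome. At a 10% CT rate, with 15–30% needing early follow-up and 75% timely, it would be 10% × (1 − 0.15 × 0.25) = 9.6% to 10% × (1 − 0.30 × 0.25) = 9.25%.

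The cost is mainly analysis text. The documents do not list CT type among the items abstracted, so a field may have to be added to the planned record review. Precision will be low, and conclusions on follow-up will be more cautious. Randomisation, sample size and patient care do not change.

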## **I. SPECIFIC AIMS**

**Specific Aim 1:** To develop a patient navigator (PN) program for lung screening for patients who are current smokers, aged 55-77 years, potentially eligible for lung screening and are receiving care at community health centers (CHCs) affiliated with MGH.

**Specific Aim 2:** To evaluate the effectiveness of the new lung screening PN program in improving screening rates and increasing use of tobacco cessation services in a randomized controlled trial.

**Specific Aim 3:** To demonstrate that equity is maintained in rates of lung screening and in follow up of abnormal chest CT results, comparing eligible smokers from CHCs with eligible smokers from other practices within the MGH primary care network.

**Specific Aim 4:** To collect quantitative data about patient satisfaction with the navigators in the lung screening PN program

**Specific Aim 5:** To explore CHC primary care providers opinions about the lung screening PN program via survey

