## **V. STUDY PROCEDURE**

### **V.1. Overview**

We propose to develop, implement, and rigorously evaluate a novel lung screening patient navigator program for patients that currently smoke in five community health centers affiliated with a primary care network of a large academic hospital.

Eligible patients will include those receiving care in community health centers who are 55-77 years old and currently smoking. The intervention trial will be randomized at the patient level. In the intervention group, patients will be contacted by a culturally competent PN who will help them stop smoking and obtain lung screening. The control patients will receive usual care. The primary outcome will assess the percentage of eligible patients in intervention and control groups who had at least one chest CT during the study period. Secondary outcomes will include as-treated primary outcomes among intervention patients contacted by the patient navigator, primary outcomes stratified by language spoken, race, age, and practice site, follow-up of abnormal results, percentage of patients with tobacco treatment, and comparison of lung screening to other practices in the primary care network.

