#### **V.4. Randomized Clinical Trial (Specific Aim 2)**

To test our hypothesis we will randomize eligible patients receiving care at CHCs to one of two study groups:

Early intervention	Usual care/delayed intervention
400 patients will receive 1:1 PN to obtain lung screening and follow-up of abnormal results, as well as smoking cessation guidance	800 patients will receive usual care during the 1-year study period. After the study period they will be offered 1:1 PN to obtain lung screening and follow-up of abnormal results as well as smoking cessation guidance

Eligibility criteria:

1. Inclusion criteria: adult patients aged 55-77 years who are current cigarette smokers (according to an algorithm using EMR data), and receive care at one of the five MGH CHCs.
2. Exclusion criteria: 1) patients who have previously received a diagnosis of lung cancer per EMR, 2) have undergone a chest CT within 18 months before enrollment, 3) are subsequently identified as having died prior to the study intervention 4) deemed by their primary care provider as not eligible for lung screening

Patients will be identified using existing electronic systems developed by the MGH Primary Care Operations Improvement (PCOI) program (Protocol # 2004P002796).

Using a newly developed TopCare smoking and lung screening registry, we will identify smokers receiving care at MGH health centers who could be eligible for lung screening. We will e-mail primary care providers a list of their patients and ask them to notify us in a week if they do not want us to contact a patient and to provide a reason why they believe patient is not eligible for lung screening. The eligible patients will then be randomly allocated to the intervention or usual care groups. Patients randomly assigned to the intervention group will be eligible for PN, while patients randomly assigned to the control will receive usual care and be eligible for navigation after the one year period.

Patient navigator intervention:

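### The unadjusted test of tobacco-medication use ignores prior treatment, so background prescriptions dilute the comparison and can cost power

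*Combined protocol and SAP*

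**What the plan says.** Specific Aim 2 (Section I) is to evaluate the navigator program in "improving screening rates and increasing use of tobacco cessation services".

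Section VI.2, item 5, turns the tobacco part into an outcome: "Tobacco treatment use: Percentage of patients, comparing intervention and control groups, who during the 1-year study period had any of the following". Three events then qualify: a Quitline referral, a medication prescription, or a referral to the health-center tobacco coach. The medication event is "smoking cessation medication prescribed in EHR (nicotine patch, gum, lozenge, inhaler, nasal spray or bupropion, or varenicline) during the study period".

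Section VI.3 (Aim 2) gives the analysis: "We will also use chi-square tests to compare the percentage with referral to MA Quitline, prescription to smoking cessation medications", followed by coach referral and smoking status. The only regression planned for Aim 2 concerns predictors of lung screening.

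On allocation, Section V.1 states: "The intervention trial will be randomized at the patient level". The eligibility list in Section V.4 admits current smokers and has no criterion on current or past cessation medication or bupropion. No section sets a look-back for prescriptions, records them at baseline, or says how the reason for a bupropion order is established.

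**The concern.** A patient already on nicotine replacement or varenicline who has it renewed in the study year scores as a success whichever arm he or she is in. So does a patient whose bupropion was ordered for something other than tobacco. Calling the drugs smoking cessation medication signals intent, but nothing makes that operational for bupropion.

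These background successes raise both percentages, and to the extent that such patients would have been prescribed the drug anyway, they shrink the difference. Prior treatment is likely to predict strongly who gets a prescription in the year, and an unadjusted chi-square treats that predictable variation as noise. At stake is the chance of detecting a real increase in the medication component, and in the any-of-three composite that contains it.

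**Working it through.** **Inputs from the documents.** 400 intervention and 800 usual-care patients (table in Section V.4). Section VI.4 instead gives a total of 1276, hence 1276 − 400 = 876 controls. Alpha is 0.05 (Section VI.4), taken as two-sided.

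**The plan's own figure.** There is none for this outcome. The 88% power in Section VI.4 is for a 5-point difference in chest CT and comes without a control rate. An assumed control rate of 5% gives 88.3% (400 v 800) or 89.2% (400 v 876). That figure does not bear on the present point.

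**Assumed inputs.** q = share of each arm with a listed prescription before randomisation. New-start rates in everyone else: s1 = 22% (intervention), s0 = 15% (control). Prescription rates in prior users during the year: r1, r0.

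**Rate and difference.** Rate in an arm = q·r + (1−q)·s. Difference = q(r1−r0) + (1−q)(s1−s0).

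**Unadjusted power** = Φ[(d − 1.96·SE0)/SE1], where SE0 = √[p̄(1−p̄)(1/n1+1/n0)] and SE1 = √[p1(1−p1)/n1 + p0(1−p0)/n0].

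*Scenario A: every prior user renews (r1 = r0 = 100%), q = 10%.*
- Intervention 0.10 + 0.90×0.22 = 29.8%; control 0.10 + 0.90×0.15 = 23.5%; d = 6.3 points, against 7.0 with no prior users. The risk ratio falls from 22/15 = 1.47 to 29.8/23.5 = 1.27.
- p̄ = 0.256, SE0 = 0.02673, SE1 = 0.02734. Power = Φ[(0.063 − 0.0524)/0.02734] = Φ(0.388) = 65%.
- Stratified by prior treatment: all prior users are successes in both arms, so that stratum contributes nothing to a Cochran-Mantel-Haenszel test. The test is 22% v 15% in 360 v 720 patients. SE0 = 0.02443, SE1 = 0.02557. Power = Φ[(0.070 − 0.0479)/0.02557] = Φ(0.865) = 80.6%.

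*Scenario B: prior users are re-prescribed at r1 = 60%, r0 = 50%, q = 10%.*
- Rates 0.06 + 0.198 = 25.8% and 0.05 + 0.135 = 18.5%; d = 7.3 points. SE0 = 0.02491, SE1 = 0.02583. Power = Φ[(0.073 − 0.0488)/0.02583] = Φ(0.936) = 83%.
- Stratified: weights n1n0/(n1+n0) are 40×80/120 = 26.67 and 360×720/1080 = 240. Weighted difference 26.67×0.10 + 240×0.07 = 19.47. Null variance 26.67×0.5333×0.4667 + 240×0.1733×0.8267 = 41.03 (SD 6.405). Variance under the alternative 26.67²×(0.24/40 + 0.25/80) + 240²×(0.1716/360 + 0.1275/720) = 44.15 (SD 6.644). Power = Φ[(19.47 − 1.96×6.405)/6.644] = Φ(1.04) = 85%.

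**Range over q, scenario A, 400 v 800**

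| q | Rates | Unadjusted | Stratified |
|---|---|---|---|
| 5% | 25.9% v 19.3% | 75% | 83% |
| 10% | 29.8% v 23.5% | 65% | 81% |
| 20% | 37.6% v 32.0% | 49% | 76% |

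With 876 controls and q = 10% the pair is 66.5% and 81.8%. With new starts of 15% v 10% (400 v 800, q = 10%, all renewing) it is 45% and 67%.

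**Would new starts be a better outcome?** Scoring prior users as 0 gives 0.90×22% = 19.8% v 0.90×15% = 13.5% at q = 10%, power 80%; at q = 20%, 74%. In scenario B the plan's any-prescription outcome has 83% and 82% even without adjustment. The ranking therefore depends on whether prior users can respond to the navigator, which the documents do not tell us.

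**The case against.** The strongest reply is that the outcome is labelled use and Aim 2 speaks of use; no section names treatment initiation as the target. Renewals are use. All participants are current smokers, so someone with an earlier cessation prescription can be treated again, and a restart prompted by the navigator is an intended effect. This stands. It rules out three inferences that a reader might draw.

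- *That the outcome hides or biases the navigator effect.* Randomisation by patient balances prior users in expectation. The comparison of use is valid; what changes is its precision and the size of the contrast.
- *That the reported percentages are simply too high.* For renewals they are not. Only bupropion ordered for another reason falls outside tobacco treatment, and its share is unknown.
- *That new starts should replace the outcome.* That changes the question, scores navigator-prompted restarts as failures, and has less power than the plan in scenario B. Counting bupropion only with a coded tobacco indication could also favour the intervention arm: Section V.4 has the navigator send patients to the PCP expressly for cessation treatment, so those orders may be labelled for tobacco more often.

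The reply also notes that full renewal is an extreme assumption. That is correct, and it is why scenario B is shown beside it. None of this defends leaving prior treatment out of the analysis: stratifying gave more power than the unadjusted test in both scenarios, with the estimand unchanged.

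**Conclusion.** The concern holds as one of efficiency and definition. The medication component has no look-back and no handling of bupropion for other indications, and its planned test ignores prior treatment. The comparison of use remains valid.

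The size is unknown, because the documents give no prescription rates. With the assumed new-start rates of 22% v 15% and 10% prior users, adjustment raises power from about 65% to 80 to 81% if all prior users renew, and from about 83% to 85% if they are re-prescribed at 60% v 50%. The gain may therefore be large or slight, depending on how strongly prior treatment predicts a prescription and whether prior users respond.

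The reach is limited to one component of a secondary outcome and the composite that includes it. The separately tested Quitline and tobacco-coach referrals are not affected.

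**What to change.** 1. In Section VI.2, item 5, keep tobacco treatment use as the outcome and say explicitly that renewals and restarts count.
2. Extract listed prescriptions for the 12 months before randomisation as a yes/no baseline variable, with bupropion recorded separately.
3. In Section VI.3, make the between-arm comparison of the medication component and of the composite stratified by that variable (Cochran-Mantel-Haenszel) or adjusted for it (logistic regression, reported as a standardised risk difference).
4. Prespecify two sensitivity analyses: new starts among patients without a prior prescription, and the result with bupropion excluded.

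The cost is one look-back in the EHR and a few lines of analysis text. That the earlier prescriptions can be retrieved is an assumption; it is reasonable because the same EHR is already to be queried for prescriptions in the study year. Excluding bupropion also drops orders genuinely made for cessation, which is why that result should stay a sensitivity analysis. The wording should be fixed before arm-level data are seen, since any of these choices would otherwise look post hoc.
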